exclusively breastfed were face-to-face contact, volunteer support, and specific schedule of four to eight contacts are more likely to succeed with women practicing exclusive breastfeeding [14]. A systematic review indicated that community based peer support for mothers is effective in increasing the duration of exclusive breastfeeding, moreover mothers are more likely to exclusively breastfeed when they receive peer support one on one or through a mother's group [15]. Therefore a feasibility randomized controlled trial (RCT) of home-based breastfeeding peer support programme was conducted by our team to determine if a future definitive RCT could be conducted to improve breastfeeding outcomes among new mothers who intend to breastfeed but have low self-efficacy on breastfeeding. Participants were recruited on a postnatal ward, eighty-five mothers were approached and 20 were screened eligible and randomly allocated into the two arms (with peer support intervention versus usual care). A higher percentage of mothers' exclusively breastfed at 1 month (44% versus 33%), 2 months (43% vs 25%) and 4 months postpartum (50% vs 33%) in the peer support arm compared to usual care. Views on the program from qualitative interviews from the participants after the intervention were positive and met their expectation. The advantages of the intervention stated by all participants were they have a point of contact in which they have someone to speak to directly about their problems. Volunteer's response is quicker and the process is faster compared with 'usual maternity care'. Peer support provided more emotional support and care which relieves pressure for first-time mothers. Participants feel more comfortable to speak with the volunteers compared to health professionals as they found nurses in hospital and clinics were too routine and more concerned with scientific or quantitative issues. These findings from the feasibility study demonstrate that women value peer supporters as mothers with similar experiences who can relate to their own situation through a shared language. Therefore, a home-based peer support intervention is recommended for the proposed study.

Summary of known and potential risks and benefits

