As intervention involves peer support (face-to-face) and no invasive procedures will be involved, risks to women and their infants are likely to be minimal. In terms of confidentiality and anonymity, analysis will take place on anonymous data. Personal identifiable data will be held separately from the anonymous data used for analysis.

Benefits include women gaining in awareness of the value of breastfeeding for their own and for their infant's health, and feeling supported in this aspect of caring for their infants.

1 Objectives and Purpose

The aim of the proposed study is to evaluate the effectiveness of a (web-based) home-based breastfeeding peer support program in improving breastfeeding practices among women with low breastfeeding self-efficacy.

2 Design

This is a two armed blinded randomized controlled trial. 442 women will be recruited from four hospitals. Trained peer counsellors will provide home based (web based due to 5th Covid wave) one-to-one breastfeeding intervention sessions to the participants.

Study Procedure

1. Recruitment:

Mother-infant pairs will be recruited from a hospital that has an average of 300+ deliveries per month. Eligible participants will be approached and invited to join the study in antenatal clinics. Women who agree to participate and sign the consent form will be invited to complete the following forms available both in Chinese or English version:

- a. Demographic Data Collection Form
- b. Breastfeeding Self-efficacy and Attitude Data Collection Form

Research assistant will complete the following form from participants' medical records:

- a. Maternal and Birth Data Collection Form

This study includes two study arms:

- a. Home-based peer support programme (web-based) and standard usual care
- b. Control group will be standard usual care

Participants will be randomized following completion of the baseline data. Block randomization procedures with random block sizes of 2, 4 or 6 will be used. An independent research assistant who will not participate in participant recruitment, data collection and analysis will generate the allocation sequence using the statistical software Stata 14. Allocation sequences will be kept in sequential numbered, opaque, sealed envelopes. Outcome assessors will be blinded to the treatment allocation. The research assistant will draw the first sealed envelope from the box and participants will be allocated to that intervention group.

2. Telephone follow-up call:

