The participants will receive follow-up telephone calls at one, two, four and 6 months postpartum. Each follow-up call will take approximately 15 minutes.

The following forms will be completed by a research assistant in the telephone follow-ups:

One month follow-up:

- a. One-Month Follow-up Data Collection Form

Two months follow-up:

- a. Two-Month Follow-up Telephone Data Collection Form
- b. Breastfeeding Self-efficacy and Attitude Data Collection Form

Four months follow-up:

- a. Four-Month Follow-up Telephone Data Collection Form
- b. Breastfeeding Self-efficacy and Attitude Data Collection Form

Six month follow-up:

- a. Six-Month Follow-up Telephone Data Collection Form

These data collection forms will be completed if needed:

- b. Weaning Data Collection Form (if participants' babies have been weaned)
- c. Return to Work Data Collection Form (if participants have return to work)

Data Sources

Data collection will consist of: (1) baseline demographic data will include data such as education, income, employment, family composition, antenatal education, (2) maternal and infant data which will include data on the mother's previous obstetrical history, delivery data and basic infant health data.

Study Outcome

Primary outcome: Infant feeding status.

Key Measures

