- **Infant Feeding Status:** Patterns of breast milk feeding as assessed at each follow up point will be classified according to existing World Health Organization definitions. Infants will be considered exclusively breastfed if they receive no solids, no non-breast milk, or no water or other liquids (other than vitamins or medications). Non-exclusively breastfed infants supplemented with infant-formula or other milk substitutes can, if required, be further classified as high partial breastfeeding (>80% of feeds are breast milk), medium-partial breastfeeding (20 to 80% of feeds are breast milk), low partial breastfeeding (<20% of feeds are breast milk). Infant feeding patterns will also be categorized according to definitions that include both the type and mode of infant feeding: (1) direct breastfeeding only, (2) expressed breast milk only, (3) direct breastfeeding and expressed breast milk feeding, (4) direct breastfeeding and formula feeding, (5) expressed breast milk feeding and formula feeding, (6) direct breastfeeding, expressed breast milk feeding, and formula feeding, and (7) formula feeding only. We will compare the overall duration of any and exclusive breastfeeding among participants in the (web-based) home-based peer support programme to the control group which received standard postnatal care only.

- **Breastfeeding Self-efficacy:** Maternal breastfeeding self-efficacy will be measured using the Breastfeeding Self-Efficacy Scale Short-Form (BSES-SF) (Chinese and English version). The BSES-SF consists of 14 items measured on a 5-point Likert scale that begin with the phrase “I can always.” On the scale 1 indicates “not at all confident” and 5 indicates “always confident.” Total scale scores range from 14 to 70 with higher scores indicating greater breastfeeding confidence and self-efficacy. We will administer the BSES-SF in baseline period and at 2 and 4 months postpartum. We will compare the scores among intervention and control groups. Permission to use the BSES-SF has been granted by the authors of both the original and Hong Kong Chinese versions.

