The team members have successfully trained 60 PCs from our previous project. The training programme comprised of 20 hours of classroom teaching and practical sessions at Queen Elizabeth Hospital and the Maternal Child Health Centres (MCHCs). The training programme was conducted by UNICEF and La Leche League covering topics such as (1) why breastfeeding is important, (2) how to assure good start of breastfeeding, (3) how to help mother breastfeeding (4) communication skills, (5) common breastfeeding problems, (6) diet and hygiene, (7) maternal illness and needs, (8) local support and role of peer counsellors. The peer counsellors were assessed by their trainers after completing the training programme. Those who pass the assessment can then carry out volunteer work using the train the trainer approach with supervision from La Leche League in MCHCs. Additional training workshop will be arranged for the PCs on solving problems of exclusive breastfeeding and correct breastfeeding technique by team leaders.

The intervention will be based on the PC programme previously conducted in our project except it will be home based (web based) peer support programme by trained PCs. In order to ensure the quality and consistency of intervention, additional training tailored to issues that may encounter in (web-based) home-based contacts will be provided to peer counsellors before the study.

The (web-based) home-based PC programme comprises of two schedules of two contacts during first month postpartum, one contact during 2 months postpartum, one contact during 4 months and one contact during 6 months postpartum, when mothers are most likely to experience difficulties with breastfeeding, and thereafter as needed. Both control and intervention groups will receive the same standard antenatal and postpartum care and a breastfeeding information leaflet. The control group will not receive home based PC programme but a breastfeeding information leaflet so the subjects will be blinded to the nature of the interventions.

5 Assessment of Efficacy

This study aims to assess effectiveness of the peer support intervention. The assessment of efficacy of the intervention will be undertaken at 1 month, 2 months, 4 months and 6 months postpartum using the criteria specified in the study outcomes.

6 Assessment of Safety

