This research involves a patient support intervention and we do not anticipate any patient safety issues. The person(s) carrying out the intervention will be trained and with experience in supporting breastfeeding women. However, as a precaution, both the delivery of the intervention and participant outcomes will be closely monitored by the PI and the study investigators

7 Statistic

Data Analysis

To compare the baseline characteristics between the two study groups, t-tests will be used for continuous variables and chi square test for categorical variables. Intention to treat analysis will be conducted. The primary outcome analyses will compare the proportions of participants in the two study groups exclusively breastfeeding at 1, 2, 4 and 6 months postpartum using chi square tests. To control for confounding factors, multiple logistic regression models will be used if required to compare breastfeeding rates between groups at the study follow up points. The secondary outcome analyses will use an independent 2-sample t tests to examine the breastfeeding self-efficacy scores and EPDS scores between the two study groups at baseline and at 1 and 3 months postpartum. To control for confounding factors, multiple linear regression models will be used to compare the scores between the groups at 3 months.

Where appropriate, each estimate will be accompanied by a 95% confidence interval and a 5% level of significance will be used in all statistical tests except where specified. The analysis will be performed using the Stata version 14.0 statistical software.

8 Direct Access to Source Data/Documents

Once data are collected, only the PI will have access to named data which will be kept locked in the PIs office in the School of Nursing. Access to the study data will be available for study related monitoring, audit and regulatory inspection by appropriate bodies. It will also be available for IRB review as appropriate.

9 Quality Control and Quality Assurance

As part of the usual review process in the department, data analysis will be reviewed by the study team to ensure it is appropriate, accurate and correctly interpreted.

10 Ethics

The main ethical considerations for this study are to ensure confidentiality to the participants and to ensure that the participants feel free to either participate in the study or to not participate in the study. The following measures will be taken to address these concerns:

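### Four monthly tests of exclusive breastfeeding are all primary at 5% each, with no rule for turning them into one conclusion

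*Combined protocol and SAP*

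**What the plan says.** The Study Outcome section gives "Primary outcome: Infant feeding status", with no month and no criterion. Section 7 (Data Analysis) turns this into four tests, which it labels primary: between-group comparisons of the proportion "exclusively breastfeeding at 1, 2, 4 and 6 months postpartum using chi square tests". It adds that "a 5% level of significance will be used in all statistical tests except where specified"; no exception is specified anywhere in the protocol.

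Section 5 (Assessment of Efficacy) says efficacy will be assessed "at 1 month, 2 months, 4 months and 6 months postpartum using the criteria specified in the study outcomes". That reference leads back to the Study Outcome section, which holds no criterion to apply.

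Under Key Measures, the infant feeding item adds a further comparison: "We will compare the overall duration of any and exclusive breastfeeding among participants". It is not ranked against the monthly proportions, and section 7 gives no method for it.

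Section 2 (Design) states that "442 women will be recruited from four hospitals". No calculation supports that number, so the sample size does not point to a primary month either.

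**The concern.** The trial asks one question: does the peer support programme improve breastfeeding practice? The plan produces four primary answers and does not say how many must be significant, or which one decides. The months and the test are fixed in advance; the step from four results to one conclusion is not. The same data could be reported as positive (some month is significant) or negative (not all months are), and that choice could be made after the results are known. Under an any-month rule, the error attached to the overall conclusion is larger than that of a single test.

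**Working it through.** **Inputs from the documents.** Four two-sided 2x2 chi-square tests, 5% each, 442 women. The Background section gives feasibility rates of exclusive breastfeeding (peer support v usual care) of 44% v 33% at 1 month, 43% v 25% at 2 months and 50% v 33% at 4 months. There is no 6-month rate.

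**Assumptions, because the documents are silent.** 1:1 allocation, so 442 / 2 = 221 per arm; Pearson chi-square without continuity correction; the rate patterns shown below; the correlation between months. The plan states no overall error rate, so there is no figure of its own to reproduce.

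**Step 1: outer limits with no true effect.**
- Independent tests, either direction: 1 - 0.95^4 = 18.5%. Simple bound: 4 x 0.05 = 20%.
- Independent tests, in favour of the programme only: 1 - 0.975^4 = 9.6%.
- Single test: 5% in either direction, 2.5% in favour.

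**Step 2: correlated months, no resumption.** If a woman who stops exclusive breastfeeding never resumes, the correlation between months s < t is sqrt[p_t(1 - p_s) / (p_s(1 - p_t))]. For 33% falling to 30% this is sqrt[(0.30 x 0.67)/(0.33 x 0.70)] = 0.93. For 50% falling to 5% it is sqrt[(0.05 x 0.50)/(0.50 x 0.95)] = 0.23. Each month uses z = (difference in proportions) / sqrt[2p(1 - p)/221], with p the pooled proportion, and is significant if |z| > 1.96. Simulated with equal rates in both arms (400,000 trials per pattern):

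| Rates at 1/2/4/6 months (%) | Any month, either direction | Any month favouring programme | All four months | Any month at 0.0125 |
|---|---|---|---|---|
| 33/32/31/30 | 0.075 | 0.037 | 0.030 | 0.020 |
| 33/30/27/25 | 0.093 | 0.046 | 0.019 | 0.026 |
| 40/35/30/20 | 0.114 | 0.057 | 0.009 | 0.032 |
| 33/25/20/10 | 0.128 | 0.064 | 0.005 | 0.035 |
| 33/25/15/5 | 0.141 | 0.070 | 0.002 | 0.039 |
| 50/35/20/5 | 0.151 | 0.076 | 0.001 | 0.041 |

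With 177 per arm (an assumed 20% loss: 221 x 0.8 = 177), the any-month figures are 0.074-0.150.

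**Step 3: resumption allowed.** Feeding status is classified afresh at each follow-up, so a woman can return to exclusive breastfeeding. This weakens the correlation. With assumed rates of 33/25/33/25% and latent correlations of 0.9, 0.7 and 0.5, the any-month figure is about 13%, 16% and 17%. Across the resumption scenarios examined it is about 12-18%, and about 6-8% in favour of the programme, moving towards the step 1 limits as correlation weakens.

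**Step 4: how often the missing rule would matter.** Assume a true 10-point difference at every month, with no resumption:

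| Scenario, rates (%) | Per arm | Any month | All four | One to three months | Any month after Holm |
|---|---|---|---|---|---|
| A: 50/45/40/30 v 40/35/30/20 | 221 | 0.79 | 0.42 | 0.37 | 0.60 |
| B: 43/35/30/20 v 33/25/20/10 | 221 | 0.90 | 0.47 | 0.43 | 0.76 |
| A | 177 | 0.71 | 0.32 | 0.39 | 0.50 |
| B | 177 | 0.84 | 0.37 | 0.47 | 0.65 |

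The fifth column is the third minus the fourth. Power at a single month with 221 per arm is 56-68% in A and 58-85% in B, depending on the month. For at least one significant month, Holm is the same as testing each month at 0.05 / 4 = 0.0125.

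**The case against.** The strongest reply is that nothing is inflated. The plan never says that one significant month counts as success. The months, the test and the exclusive breastfeeding definition are fixed in advance, and 95% confidence intervals are promised where appropriate. Reported as four separate monthly comparisons, each test has its nominal 5% error. This stands: a reader might infer that the plan adopts an any-month rule, but it adopts no rule at all. The defect is that absence, and the error rates are conditional on how the gap is filled.

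A reader might also take 7-15% as the chance of wrongly concluding that the programme works, or infer that this chance always exceeds 5%. Neither follows. About half of the false significant results would show the programme doing worse. For a false claim of benefit the no-resumption range is 3.7-7.6%, and two of the six patterns (3.7% and 4.6%) lie below 5%. The proper comparison is the 2.5% of a single test in that direction, which all six exceed.

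Nor is 7-15% a bound. It depends on no woman resuming, which the outcome definition does not require. The feasibility rates rise between months 2 and 4 in both arms (43% to 50%; 25% to 33%). With 20 women a changing denominator could explain that, but the figures give strict nesting no support. In the other direction, a Yates-corrected chi-square would lower the no-resumption range to about 6-12%.

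**Conclusion.** The concern holds as a missing decision rule for the primary outcome, and that part depends on no assumption. Its size under an any-month reading is illustrative. The chance of at least one false significant month is about 7-15% without resumption and about 12-18% with it, and 18.5% under independence. For a false claim of benefit it is 3.7-7.6% or about 6-8%, against 2.5%. These figures assume 1:1 allocation, an uncorrected chi-square and the stated rate patterns. The opposite reading, that all four months must be significant, is conservative: 0.1-3.0% in the same no-resumption patterns. Mixed results would be common under a true 10-point difference: about 37-43% of trials at 221 per arm and 39-47% at 177.

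**What to change.** Before any outcome data are seen, amend the Study Outcome section and section 7 to name one primary analysis tested at 5%. The investigators should choose it on clinical grounds and not from the feasibility study, in which "eighty-five mothers were approached and 20 were screened eligible and randomly allocated into the two arms". Three options would each give a single conclusion:

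- exclusive breastfeeding at one named month;
- one comparison of exclusive breastfeeding duration, which Key Measures already plans but for which section 7 must add a method;
- one joint test over the four months, with its form stated.

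The remaining comparisons become secondary and are still reported.

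If all four months stay primary, apply Holm and state that success means at least one month significant in favour of the programme after adjustment.

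The cost is a protocol amendment to the primary outcome; no extra women, visits or data are needed. With a single primary month, significance at another month no longer counts as primary success. Power at the chosen month cannot be confirmed, because the basis of 442 is not stated. With Holm, power for at least one significant month falls from 79% to 60% in scenario A and from 90% to 76% in scenario B (221 per arm). Holm also over-corrects when months are strongly correlated: its familywise error is 2.0-4.1% in the no-resumption patterns. Power for the duration and joint-test options was not evaluated here.

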- **Edinburgh Postnatal Depression scale:** Participant’s postpartum depression symptoms will be measured by EPDS, Chinese version. It is an instrument consisting of 10 simple and easily understood items, with rating on a scale from 0 to 3, yielding a total range of 0 to 30. EPDS was developed by Cox et al (1987) and has been widely used for the assessment of postnatal depressive symptoms, but it is not a diagnostic scale for depression, rather a screening tool for those vulnerable to developing depression. The Chinese version of EPDS has been validated and shown to have high sensitivity in detection of postnatal depression. To evaluate the postpartum depressive symptoms, pre (1 month postpartum) and post (2 months postpartum) EPDS will be compared between the two groups.

3 Selection and Withdrawal of Subjects

Study population

To be eligible for inclusion in the RCT, participants must be (1) 18 years of age or older, (2) primiparous mothers, (3) intention to breastfeed, (4) low breastfeeding self-efficacy score (between 14 and 32), (5) singleton pregnancy, (6) term infant (37-42 weeks gestational), (7) Cantonese speaking, (8) HK resident and (9) mother with no serious medical or obstetrical complications.

Participants will be excluded from the study if they fail to meet these criteria and/or if their baby: (1) is <37 weeks gestation, (2) has an Apgar score <8 at five minutes, (3) has a birthweight <2500 grams, (4) has any severe medical conditions or congenital malformations, (5) is placed in the special care baby unit for more than 48 hours after birth, or (6) is placed in the neonatal intensive care unit at any time after birth.

4 Treatment of Subjects

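### Nothing in the plan commits to adjusting BSES-SF for its baseline score: the t-tests have no baseline term, and the single regression names no covariates

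*Combined protocol and SAP*

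**What the plan says.** Section 7 (Statistic, Data Analysis) gives the method for the secondary scores: "The secondary outcome analyses will use an independent 2-sample t tests to examine the breastfeeding self-efficacy scores", together with the EPDS scores, at baseline and at 1 and 3 months. The next sentence adds an adjusted analysis: "To control for confounding factors, multiple linear regression models will be used to compare the scores between the groups at 3 months". It lists no covariates. Section 7 does not say whether the t-test or the regression supplies the reported result, and it plans no adjusted model for the earlier time point.

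Three other places bear on the point:

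- Section 2, Study Procedure (Recruitment) lists the self-efficacy form among those completed on joining the study, and adds: "Participants will be randomized following completion of the baseline data".
- Section 3 makes the same score an eligibility condition: "low breastfeeding self-efficacy score (between 14 and 32".
- Key Measures sets the schedule: "We will administer the BSES-SF in baseline period and at 2 and 4 months postpartum". It also gives the range: "Total scale scores range from 14 to 70 with higher scores indicating greater breastfeeding confidence and self-efficacy". The telephone follow-up list agrees, placing the self-efficacy form at the two- and four-month calls.

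**The concern.** The same 14-item scale is taken before randomisation and again at follow-up. A two-sample t-test on follow-up scores makes no use of the first measurement. If the two scores are correlated, the interval for the arm difference is wider than it need be, and any chance difference between arms at baseline passes in part into the estimate. Section 2 mentions no stratification by baseline score that would limit such a difference.

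The regression may or may not close this gap, because its covariates are not stated. As written, the choice of covariates, and of which result to report, could be made after the data are seen. At stake are the precision and the pre-specification of a secondary outcome. The infant feeding analysis is not affected.

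The point is confined to BSES-SF. EPDS is first measured at 1 month, when peer contacts are already scheduled, so it has no pre-randomisation score to adjust for.

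**Working it through.** **Inputs from the documents.** Section 2 gives the total: "442 women will be recruited from four hospitals". Section 7 gives a 5% significance level and 95% confidence intervals. Baseline BSES-SF is limited to 14 to 32 on a scale of 14 to 70.

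**Assumptions.** Allocation 1:1 (221 per arm), two-sided testing, complete follow-up, and a correlation r between baseline and follow-up BSES-SF. The documents give no r, so a range is shown. They also give no power, effect size, SD or dropout for 442, and no figure for the BSES-SF comparison, so there is no stated result to reproduce.

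**Step 1: unadjusted interval.** In outcome SD units the standard error is √(2/221) = 0.0951, and the 95% half-width is 1.96 × 0.0951 = 0.186.

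**Step 2: adjusting for baseline.** Residual variance falls by the factor 1 − r², so the half-width is 0.186 × √(1 − r²). The number of women a t-test would need for the same width is 442/(1 − r²). Power is for an illustrative difference of 0.25 SD, which is not a figure from the plan; the t-test gives 74.8%.

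| r (assumed) | √(1 − r²) | Half-width (SD) | Narrower by | Equivalent women (extra) | Power |
|---|---|---|---|---|---|
| 0.2 | 0.980 | 0.183 | 2.0% | 460 (18) | 76.5% |
| 0.3 | 0.954 | 0.178 | 4.6% | 486 (44) | 78.7% |
| 0.4 | 0.917 | 0.171 | 8.3% | 526 (84) | 81.8% |
| 0.5 | 0.866 | 0.161 | 13.4% | 589 (147) | 85.9% |

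**Step 3: which rows are plausible.** Restricting the baseline range lowers the correlation. With R the unrestricted correlation and u the ratio of restricted to unrestricted baseline SD, r = R·u/√(1 − R² + R²u²). For R = 0.5 and u = 0.4, 0.6 and 0.8 (all assumed), r = 0.225, 0.327 and 0.419. At the two ends √(1 − r²) is 0.974 and 0.908, so the interval narrows by about 3% to 9%. This favours the upper rows of the table over the last.

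**Step 4: chance baseline gap.** The 95% limit on the difference in baseline means is 1.96 × SD × 0.0951. For an assumed baseline SD of 3 this is 0.56 points. For 5.48, the SD if scores were spread evenly over the 19 integers from 14 to 32 (√((19² − 1)/12)), it is 1.02 points. The part carried into the t-test estimate has standard error r × 0.0951, which is 0.019 outcome SD at r = 0.2 and 0.048 at r = 0.5, within the total of 0.095.

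**Step 5: months.** Section 7 analyses BSES-SF at 1 and 3 months; it is collected at 2 and 4 months. Neither the follow-up t-tests nor the regression matches a BSES-SF score that will be collected.

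**The case against.** The best defence is that the plan already contains an adjusted analysis. The linear regression is promised without condition, whereas the logistic models for feeding are to be used only if required. It could include baseline BSES-SF. This stands: a reader might infer that the plan ignores baseline altogether, and the documents do not support that. They leave the covariates open at one time point and plan no adjusted model at the other. Nor can the t-test be called the plan's main analysis, since section 7 ranks neither method above the other.

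The t-test is also not wrong. It is unbiased over randomisations, holds its 5% error rate, and its confidence interval already allows for chance imbalance. A reader who inferred bias or an invalid test would be going too far.

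The gain may be small. Entry covers only the bottom of the scale, the women are first-time mothers approached in antenatal clinics, and the next score comes at 2 months postpartum. No document compares baseline BSES-SF with other predictors, so it cannot be called the best one available. Self-efficacy defines the population, but the stated aim is to improve breastfeeding practices; that self-efficacy is the mechanism of the programme would be an inference. These points limit the size and importance of the gain. They do not remove it, because the score is collected anyway.

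Finally, the mismatch of months is the more serious defect in the same paragraph and must be settled first. That is right, but settling it would not put a baseline term into the t-tests or name covariates for the regression.

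**Conclusion.** The point holds in a limited form. The t-tests carry no baseline term, the one regression covers a single time point with unnamed covariates, no analysis is designated as the main one, and nothing commits the plan to using a baseline score that every randomised woman should have.

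The consequence is modest lost precision on a secondary outcome: intervals that adjustment would narrow by about 2% to 8% for r of 0.2 to 0.4, and by about 13% at 0.5. Adjustment would also remove the part of any chance baseline gap that is linearly related to the outcome. The direction is certain for any non-zero r, apart from the negligible cost of one extra parameter at this sample size. The size rests on an assumed r and on 442 women with complete follow-up. The 147-women equivalent at r = 0.5 should not be taken as the expected gain, because truncation to 14 to 32 makes the lower values more plausible.

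**What to change.** First reconcile the BSES-SF analysis months in section 7 (1 and 3) with the collection months in Key Measures and the telephone follow-up list (2 and 4).

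Then state in section 7 that the main BSES-SF analysis is analysis of covariance at each collected month: linear regression of the follow-up score on arm and baseline BSES-SF. One mixed model for both months, with baseline BSES-SF as covariate and the arm difference estimated at each month, would serve equally well. Name any further covariates now. Report the adjusted mean difference with its 95% confidence interval, and keep the unadjusted t-test as supportive only.

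Dropping the between-arm significance test of baseline BSES-SF is optional. After randomisation any difference it finds is due to chance, and removing it changes no treatment estimate. If it is kept, it should not guide the choice of covariates.

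The cost is a sentence or two in section 7. No new data, visits or forms are needed.
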